5.10. Second Key Secondary Efficacy Analysis

The second key secondary efficacy endpoint is the 50% responder rate, defined as the percent of subjects with at least a 50% reduction in the Maintenance Phase focal onset seizure frequency rate relative to the Baseline Period.

5.10.1. Second Key Secondary Estimand

The key research question for the second key secondary efficacy variable will be addressed with an estimand based on the following attributes:

- 1. Treatments: treatments as randomized regardless of the actual treatment received.
- 2. Target study population of interest: subjects in the modified intent-to-treat (mITT) population.
- 3. Endpoint (variable) of interest: 50% responder rate in the Maintenance Phase.

- 4. Population level summary of interest: the 50% responder rate in the Maintenance Phase relative to the baseline period between CVL-865 treated and placebo subjects.
- 5. Strategy for Intercurrent events (ICEs): a hypothetical strategy will be used to address intercurrent events (ICEs) of potential death, and treatment discontinuations. The data after treatment discontinuations will typically be missing or be treated as missing even if collected. These missing values as the result of ICEs of discontinuation will be assumed to follow the observed trajectory of the subject and thus the endpoint will include only eDiary based response data that occur before discontinuation of treatment. However, subjects with greater than 80% missing seizure diary entries will be treated as non-responders. It should be noted that the use of protocol defined rescue medication will not be considered as an ICE.

5.10.2. Main Analytical Approach for Second Key Secondary Endpoint

The second key secondary endpoint, 50% responder rate, will be analyzed for the mITT population using a logistic regression model with effects for treatment and baseline seizure frequency. The binary outcome will be defined as having at least a 50% reduction in the maintenance phase relative to the baseline period or not having a 50% reduction. Odd ratios will be constructed for each CVL-865 treatment dose group compared with placebo and will be summarized with 90% confidence intervals. Subjects with greater than 80% missing seizure diary entries will be treated as non-responders for this analysis. Should a logistic regression model fail to converge, paired Fisher's exact tests will be used instead.

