An additional key secondary endpoint is the 50% responder rate, defined as the percentage of subjects with at least a 50% reduction in the Maintenance Phase focal onset seizure frequency relative to the Baseline Period. This key secondary endpoint will be analyzed for the mITT population using a logistic regression model with effects for treatment. Odds ratios representing the odds of being a responder compared with placebo will be constructed for each CVL-865 treatment group. Subjects with missing or incomplete seizure information will be treated as non-responders for this analysis.

Continuous endpoints with repeated post-baseline assessments (CGI-S, CGI-I, PGIC) will be analyzed for the mITT population using a Mixed Model for Repeated Measures (MMRM). This estimand will include available post-baseline response data that occur before discontinuation of treatment. The baseline score (if applicable) will be included as the covariate, and treatment group (CVL-865 7.5 mg, CVL-865 25 mg, or placebo), visit, and the interaction between treatment group and visit will be included as fixed factors in the MMRM. The difference between each CVL-865 level versus placebo at each visit will be estimated based on the LSMeans from the MMRM. Changes from baseline in QOLIE-31 Domain and Overall Scores and HUI Utility Function scores will be analyzed using an analysis of covariance model (ANCOVA) with the baseline score and treatment group included in the model as fixed effects. The difference between each CVL-865 level versus placebo will be estimated based on the LSMeans from the ANCOVA model.

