1.1. Study Overview

This is a double-blind, parallel-group, placebo-controlled trial with subjects randomized to 1 of the following 3 arms in a 1:1:1 ratio:

- CVL-865 25 mg BID maintenance
- CVL-865 7.5 mg BID maintenance
- Placebo

This maximum duration is to be approximately 25 weeks, consisting of the following:

- 8-week Screening/Baseline Period
- 10- or 13-week Treatment Period, including an initial 2-week Titration Phase, an 8-week Maintenance Phase, and a 3-week Taper Phase (only for subjects not continuing treatment in the open-label extension trial). The tablets (including the number of tablets given) will be the same between the placebo and both CVL-865 dose arms during the Titration, Maintenance, and Taper Phases to maintain the blind
- 4-week Follow-up Period (only for subjects not continuing treatment in the openlabel extension trial)

Subjects are to continue on their current AEDs at the same dosages throughout the Screening/Baseline Period. If a subject has a vagus nerve stimulator (VNS), a deep brain stimulator (DBS), or a responsive neurostimulator (RNS), the settings must remain stable throughout the Screening/Baseline Period.

During this Screening/Baseline Period, subjects will be required to complete electronic seizure diaries (eDiary) and record all seizures in the eDiary for each day and days free of seizures. The presence or absence of all seizure types experienced by each subject will be recorded daily in the eDiary.

Subjects who satisfy all inclusion/exclusion criteria and thus are eligible for the trial will be randomized to 1 of 3 treatment arms at Visit 1 (Day 1). The daily dosing schedule will start at Day 1 with a 2-week Titration Phase during which time the subject's dose will be increased in a blinded fashion up the randomized dose level (CVL-865 25 mg BID, CVL-865 7.5 mg BID, or placebo). In the high-dose group, CVL-865 will be administered as

during the Titration Phase, and then 25 mg BID during the 8-week Maintenance Phase. In the low-dose group, CVL-865 will be administered as

during the Titration Phase, and then

7.5 mg BID during the 8-week Maintenance Phase.

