3.1. Efficacy Assessments

3.1.1. Seizure Frequency and Type (eDiary)

Subjects will record details regarding their seizures (frequency and type) in an eDiary. Any BZD use will also be recorded in the diary. Seizure frequency and type will be assessed based on information recorded by the subject in the eDiary.

Seizure frequency is defined as the total number of focal onset seizures over the analysis period of interest divided by the total number of days with no missing seizure counts in the corresponding period multiplied by 7. For cluster seizures, which are a group of seizures too numerous to count, the number of cluster episodes will be included as one seizure event. Unless otherwise specified, Seizure frequency will only be calculated for focal onset seizures, which include focal aware seizures without motor signs, focal aware seizures with motor signs, focal impaired awareness seizures and focal to bilateral tonic-clonic seizures.

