4.2. Analysis Periods

The start and end dates of each analysis period (following the study design) are used for the classification of efficacy data. The exact start and end of each of these periods is described for calculation purposes in Section 4.3. Seizure frequency and average daily dose for each analysis period will be calculated based on Table 3.

Table 3:	Definition of Analysis Periods for Seizure Frequency and Average Daily Dose
	Data

Analysis Period	Duration	Start Date	End Date
Baseline Period	~8 Weeks	The greater of: Study Day, -56 or Informed consent	Study Day, -1
Titration Phase	~2 Weeks	Study Day, 1	The lesser of: Day 15 (Visit 2) minus 1 or *Early termination (minus 1) or End of Treatment
Maintenance Phase	~8 Weeks	Day 15 (Visit 2)	The lesser of: **Day 71 (Visit 4) minus 1 or *Early termination (minus 1) or End of Treatment
Taper Phase	~3 Weeks	Day 71 (Visit 4) or *Early termination	End of Treatment

* If a subject experiences early termination from the study and continues to Taper Phase, end dates will be bound by early termination minus 1 while the start of Taper Phase will begin on the date of early termination. ** For subjects continues to Taper Phase from Maintenance Phase

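### The SAP scores subjects who stop drug during Maintenance as 50% responders or not on their pre-stop diary days, departs from the protocol's non-responder rule without saying so, and gives no denominator for its 80% threshold

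*SAP*

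**What the plan says.** Protocol 9.4.1 sets the rule for the responder endpoint without a threshold: "Subjects with missing or incomplete seizure information will be treated as non-responders for this analysis". It does not define what makes a record incomplete.

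SAP 5.10.1 (item 5) adopts a hypothetical strategy for treatment discontinuation: "These missing values as the result of ICEs of discontinuation will be assumed to follow the observed trajectory of the subject". In practice, a subject who stops is classified on the diary days up to the stop. The one exception appears in 5.10.1 and again, for the logistic model, in 5.10.2: "Subjects with greater than 80% missing seizure diary entries will be treated as non-responders for this analysis". Neither section gives the period or the denominator for the 80%.

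Three other SAP sections decide what happens to a short record:

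- Section 3.1.1: the seizure count is "divided by the total number of days with no missing seizure counts in the corresponding period multiplied by 7", so any number of diary days yields a weekly rate.
- Section 4.2 (Table 3 footnote): for a subject who terminates early, "end dates will be bound by early termination minus 1".
- Section 5.7.1: diary compliance is computed only over the time the subject actually took part.

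The SAP mITT (5.2) needs just one Maintenance diary entry. Subjects who stop during Titration are therefore outside the analysis, and the point concerns Maintenance-phase stops only.

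**The concern.** One endpoint has two scoring rules. A subject whose seizures halve for two or three weeks of Maintenance and who then stops for intolerance is a failure under the protocol and a success under the SAP. These answer different questions: response while on drug, or response together with staying on drug to the end of Maintenance.

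The SAP rule also applies the 50% cut to short records, where the expected seizure count may be only two or three and chance alone often crosses the line. With the 80% denominator unstated, two programmers could classify the same subject differently, and the choice could be made after the data are seen.

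**Working it through.** **No stated figure for this endpoint.** The plan's only power claim is for RRatio. It reproduces at 40 evaluable per arm: 20 / (34 × √(2/40)) = 2.63; 2.63 − 1.645 = 0.986; power 83.8%, in line with the stated minimum of 80%. Nothing comparable is given for the responder rate.

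**1. Where the 80% rule bites.** The design is "including an initial 2-week Titration Phase, an 8-week Maintenance Phase, and a 3-week Taper Phase", so Maintenance is 8 × 7 = 56 days.

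- Planned-days denominator: 11 diary days leave 45/56 = 80.4% missing, a forced non-response. 12 diary days leave 44/56 = 78.6% missing, so the subject is scored on the data.
- Actual-participation denominator (SAP 4.2 and 5.7.1): a subject who fills in every day and stops after d Maintenance days has 0/d = 0% missing for any d. The rule never applies.

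**2. Chance response on a short record.** Assumptions: Poisson counts, the same true rate in Baseline and Maintenance, and a 56-day Baseline count b of at least 8 (Protocol 5.1, criterion 4). A subject with T seizures in d days is a responder if T/d ≤ 0.5 × b/56. Weekly rates are assumed.

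| True rate per week | 12 days | 14 days | 28 days | 56 days |
|---|---|---|---|---|
| 1 | 34% | 41% | 28% | 18% |
| 2 | 19% | 18% | 9% | 4% |
| 4 | 9% | 8% | 3% | 0.5% |
| 5 | 7% | 6% | 1% | 0.2% |

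As a hand check at 1 per week over 14 days: for b from 8 to 15 the cut is T ≤ 1, and P(T ≤ 1) with mean 2 is 3e⁻² = 41%. The 12-day figure lies below the 14-day figure at this rate because counts are whole numbers: for b of 8 or 9 over 12 days, only T = 0 qualifies.

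**3. Effect on the arm contrast.** Assumptions: completers respond at 20% (placebo) and 40% (active); a share q of Maintenance stoppers, equal in both arms, is scored as responding under the SAP. Protocol-rule rate = completer rate × (1 − stop rate). SAP-rule rate = that value + q × stop rate. q runs from 20% to 40%.

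| Stops, placebo / active | Protocol rule | SAP rule |
|---|---|---|
| 20% / 20% | 16% vs 32%, OR 2.47 | 20–24% vs 36–40%, OR 2.25–2.11 |
| 10% / 30% | 18% vs 28%, OR 1.77 | 20–22% vs 34–40%, OR 2.06–2.36 |

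With equal stops the difference is 16 points under both rules and the SAP odds ratio is the smaller. With more stops on active, the SAP rule gives 14 to 18 points against 10. The documents state 20% dropout overall and no split by arm or phase.

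**4. What the sensitivity analyses reach.** SAP 5.10.3 rebuilds the responder rate from two analyses in 5.8.4.

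- Imputation under missing at random when more than 50% of a period's entries are missing. Over 56 days that means 27 or fewer diary days (29/56 = 51.8% missing). Over actual participation a compliant early stopper is again not reached.
- Jump to reference for discontinuation up to Visit 3 (Day 43, which is Maintenance Day 43 − 15 + 1 = 29), for seizure adverse events, subject withdrawal, lack of efficacy or loss to follow-up. Stops for other adverse events, and every later stop, fall outside.

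Neither scores discontinuation as non-response, so the protocol's rule is not run anywhere.

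**The case against.** The SAP's approach can be defended. Item 5 of 5.10.1 declares a hypothetical strategy openly, and it matches the primary and first key secondary estimands. Protocol 9.4 leaves missing-data procedures to the SAP. Read literally, the protocol's sentence is unworkable: one missed diary day would fail a subject, and at an assumed 98% independent daily compliance only 0.98^56 = 32% of subjects would have a full record. That also sits badly with the protocol's own frequency formula, which divides by non-missing days. Counting every stop as failure would include exits unrelated to treatment, such as the COVID-19 terminations that Protocol 9.2 foresees. The sensitivity analyses test part of the assumption, and SAP 5.4 calls the study exploratory, with no multiplicity control.

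Most of this stands. It shows that the hypothetical strategy is a legitimate choice and that some tolerance for missed days is needed. It does not explain why an explicit protocol rule was dropped without comment, it does not supply the 80% denominator, and it does not cover stops for non-seizure adverse events or after Visit 3 in the jump-to-reference analysis.

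A reader might take SAP section 6 as showing that the change was concealed. It does not. That section concerns later deviations from the approved SAP, to be reported in the study report; it is not a list of differences from the protocol.

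**Conclusion.** The discrepancy is real. A subject who stops during Maintenance has an incomplete record on any ordinary reading of Protocol 9.4.1, yet the SAP can score that subject a responder on 12 of 56 days, or on a few days if the denominator is actual participation. Chance response on such records is material at 1 to 2 seizures per week, near the eligibility floor, and small from about 4 per week. Those figures assume Poisson counts and no true change.

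A reader might infer that the SAP rule biases the endpoint towards active drug. The documents do not support that as a general statement. It follows if stops are more frequent on active; with equal stops the odds ratio, which is the SAP's measure, can shrink. The arm-level figures rest on assumed responder rates and stop splits and illustrate the direction only. Nor do the documents show that the main analysis must be replaced. What is missing is a defined threshold, an analysis that applies the protocol's rule in workable form, and a statement of the change.

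**What to change.** 1. In SAP 5.10.1 and 5.10.2, compute the 80% over the planned 56 Maintenance days.
2. In SAP 5.10.3, add a pre-specified analysis with the same logistic model in which mITT subjects who discontinue IMP before Visit 4 are non-responders. Occasional missed diary days in subjects who complete Maintenance do not count. Report it beside the main result.
3. State in the SAP that the main rule differs from Protocol 9.4.1, and why.

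Making the second analysis the main one is optional.

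Cost: a few sentences and one extra logistic model, with the possibility of a less favourable responder difference. The added analysis will also count some treatment-unrelated exits as failures, which is a reason to present both results together.

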5.10.3. Sensitivity Analyses

The sensitivity analyses to assess the impact of low eDiary compliance and that of discontinuation potentially related to treatment described in Section 5.8.4 for the primary estimand will also be performed for the second key secondary efficacy estimand. The 50% responder rate will be constructed off the results from the primary sensitivity analysis. This will be conducted for the two different sensitivity assessments will be conducted to assess the impact of this missingness (data are missing at random and data are not missing at random).

5.11. Other Efficacy Analyses

5.11.1. Other Secondary Efficacy Endpoints

Other protocol-defined secondary efficacy endpoints will be summarized using descriptive statistics by treatment group and visit, if appropriate. Statistical analysis method for each endpoint is described below in Table 11. Statistical comparisons for each endpoint will be constructed without adjustment for multiple endpoints.

Table 11:	Summary of Other Secondary Efficacy Analyses

Endpoint	Analysis Population	Analysis Method
Seizure Freedom	mITT	Seizure freedom is defined as no seizures during the maintenance period. A logistic regression model with treatment as a fixed effect will be used. Odd ratios will be constructed for each CVL-865 treatment dose group compared with placebo and will be summarized with 90% confidence intervals. Should a logistic regression model fail to converge, paired Fisher's exact tests will be used instead.
Seizure Rate over Time	mITT	Seizure rate over time during the maintenance period will be analyzed using an MMRM. Only focal onset seizure will be included in this analysis. Data will be log-transformed using the convention ln(X+1), where X represents the seizure rate at each time point. Treatment group (CVL-865 7.5 mg, CVL-865 25 mg, or placebo), visit, and the interaction between treatment group and visit will be included as fixed factors in the MMRM, and log-transformed baseline rate will be included as a covariate. Subject will be included as a random effect, and an unstructured covariance structure will be used for the repeated measures. The difference between each CVL-865 level versus placebo at each visit will be estimated based on the LSMeans from the MMRM. The model estimated mean percent change from baseline and percent reduction versus placebo at each visit will be derived from back-transformed statistics the same way as described in Section 5.9.3 . A Mann-Whitney U test will also be used to compare each treatment level versus placebo at each visit.
PGI-C Score at Visits 2, 3, and 4	mITT	PGI-C score over time will be analyzed using a Mixed Model for Repeated Measures (MMRM) analysis. Treatment group (CVL-865 7.5 mg, CVL-865 25 mg, or placebo), visit, and the interaction between treatment group and visit will be included as fixed factors in the MMRM. Subject will be included as a random effect, and an unstructured covariance structure will be used for the repeated measures. The difference between each CVL-865 level versus placebo at each visit will be estimated based on the LSMeans from the MMRM.
CGI-S Score - Change from Baseline to Visits 2, 3, and 4	mITT	Change from baseline in CGI-S score over time will be analyzed using similar MMRM model as described above for PGI-C score.
CGI-I Score at Visit 2, 3, and 4	mITT	CGI-S score over time will be analyzed using similar MMRM model as described above for PGI-C score.
QOLIE-31 Overall and Domain Score - Change from Baseline to Visit 4	mITT	Changes from baseline in QOLIE-31 Overall Scores will be compared using an ANCOVA model with the baseline score as a covariate and treatment group included in the model as fixed effects in the mITT population. This estimand will include available post-baseline response data that occur before discontinuation of treatment or addition of rescue medication. The differences between each treatment dose group and placebo will be estimated based on the LSMeans difference between each CVL-865 dose group and placebo with corresponding 90% CI. The QOLIE-31 Domain Scores will be analyzed the same way, by each of the following categories: Energy, Emotions, Daily

Endpoint	Analysis Population	Analysis Method
		Activities, Mental Activity, Medication Effects, Seizure Worry, and Overall Quality of Life.
HUI Utility Score - Change from Baseline to Visit 4	mITT	Overall Health-Related Quality of Life (HRQL) Utility Scores (HUI-3 and HUI-2) will be analyzed using an ANCOVA model as described above for QOLIE-31 Overall Scores.

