# 9.4 Statistical Analyses

Descriptive statistical methods will be used to summarize the data from this study, with statistical testing performed for the efficacy endpoints. Unless stated otherwise, the term "descriptive statistics" refers to number of subjects (n), mean, median, standard deviation, minimum, and maximum for continuous data, and frequencies and percentages for categorical data. Statistical testing, if performed, will be 2-sided and will be performed using a significance (alpha) level of 0.1. All available data for enrolled subjects will be listed by subject. Unless otherwise noted, the data will be sorted first by subject number and then by date within each subject number.

All statistical analyses will be conducted with the SAS® System, version 9.4 or higher.

The remainder of this section is a summary of the planned statistical analyses of the primary and secondary endpoints as well as a description of planned safety analyses. Full details of these analyses will be included in the statistical analysis plan (SAP). The SAP will be developed and finalized before database lock and will describe the subject populations to be included in the analyses, and procedures for accounting for missing, unused, and spurious data.

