5.5. Strata and Covariates

No stratification was implemented in randomization. The baseline value of each efficacy variable will be included as a covariate in the efficacy analyses.

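### The seizure-freedom model omits baseline seizure rate and has no firm rule for an arm with no seizure-free subject; a penalised, baseline-adjusted model is a cheap improvement

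*SAP*

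**What the plan says.** SAP 5.11.1, Table 11, defines the endpoint: "Seizure freedom is defined as no seizures during the maintenance period". The mITT analysis is described as follows: "A logistic regression model with treatment as a fixed effect will be used". Odds ratios for each dose against placebo are to be "summarized with 90% confidence intervals". The fallback reads: "Should a logistic regression model fail to converge, paired Fisher's exact tests will be used instead". I take paired to mean pairwise, each dose against placebo. No penalised or exact logistic method is named, so ordinary maximum likelihood is inferred.

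SAP 5.5 sets a general rule: "The baseline value of each efficacy variable will be included as a covariate in the efficacy analyses". For the other binary seizure endpoint, the 50% responder rate, SAP 5.10.2 specifies a "logistic regression model with effects for treatment and baseline seizure frequency". The seizure-rate MMRM in Table 11 carries the log-transformed baseline rate.

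Protocol 9.4.1 names no method for seizure freedom. Protocol 9.4 fixes the test level: "Statistical testing, if performed, will be 2-sided and will be performed using a significance (alpha) level of 0.1". Neither document gives an expected seizure-free rate, or a power, for this endpoint.

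**The concern.** Inclusion criteria 4 and 5 require at least 8 focal seizures in the 8-week baseline, no 21-day seizure-free stretch, and failure of at least two anti-epileptic drugs. A low seizure-free rate over an 8-week Maintenance Phase is therefore plausible, particularly on placebo.

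If no placebo subject is seizure-free, the maximum-likelihood log odds ratio runs to infinity for both dose comparisons, and the promised odds ratio with its interval cannot be reported. The switch to Fisher depends on whether the fitting routine reports non-convergence. With complete separation that varies with the software and its tolerance, so the choice of test could be made after unblinding.

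It is also reasonable to expect that subjects who enter with low seizure rates are those most able to become seizure-free. A chance imbalance in baseline rate would then go uncorrected here, although the plan corrects for it in the other seizure-diary models.

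**Working it through.** **The plan's own figure.** The only stated power is at least 80% for the primary RRatio comparison (difference 20, SD 34, two-sided 0.10, 50 randomised per arm, 20% dropout, hence 40 evaluable). The normal approximation gives 20 / (34 × √(2/40)) = 20 / 7.60 = 2.63; 2.63 − 1.645 = 0.99; power 83.8%. The figure reproduces, but says nothing about seizure freedom.

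**Inputs.** From the documents: two-sided 0.10, 40 evaluable or 50 randomised per arm, 1:1:1 allocation, and the model and fallback quoted above. Assumed: placebo seizure-free rates of 1-5% and active rates of 10-20%.

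**Step 1: chance of an empty placebo cell.** P(0 events) = (1 − p)^n.

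| Placebo rate | n = 40 | n = 50 |
|---|---|---|
| 1% | 67% | 61% |
| 2% | 45% | 36% |
| 3% | 30% | 22% |
| 5% | 13% | 8% |

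**Step 2: size of the planned test.** With treatment as the only term, each dose-placebo contrast is a 2×2 table, so all tables can be enumerated exactly. The planned test is taken as the logistic Wald test, with Fisher for every table that has a zero cell. This is the reading most favourable to the plan. Probability of rejecting at nominal 10% when both arms share the rate:

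| Common rate | n = 40 | n = 50 |
|---|---|---|
| 1% | 0.0% | 0.0% |
| 2% | 0.1% | 0.3% |
| 3% | 0.5% | 1.0% |
| 5% | 2.2% | 3.3% |
| 10% | 7.5% | 7.3% |

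With no placebo events, Fisher needs 5 active events (p = 0.055 at n = 40, 0.056 at n = 50), since 4 give p = 0.116 and 0.117. Unadjusted Firth rejects at 4.

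**Step 3: effect of the trigger.** If a zero-cell fit is accepted as converged, its Wald test cannot reject. A Newton-Raphson fit of 0/45 versus 5/45 gives a coefficient of about 20.8, SE about 14,000 and p = 0.999, where Fisher gives 0.056. Exact power at n = 40:

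| Placebo vs active | Fisher for every zero cell | Zero-cell Wald accepted |
|---|---|---|
| 1% vs 10% | 31% | 6% |
| 2% vs 10% | 26% | 9% |
| 2% vs 15% | 60% | 27% |

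**Step 4: comparison with the alternative.** Firth logistic regression with log baseline rate was simulated, 1,200 runs per case. Assumed: log baseline rate normal (median 2.5 per week, SD 0.9), truncated at 1 per week (8 seizures in 8 weeks), with log-odds slope −1 or −2. Monte Carlo standard error is at most √(0.25/1200) = 1.4 points. The planned test again has Fisher for every zero cell. Where two values are shown, they are for the two slopes.

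| Placebo vs active | Planned, n = 40 | Firth + log baseline, n = 40 | Gain, n = 40 | Gain, n = 50 |
|---|---|---|---|---|
| 1% vs 10% | 31-33% | 53-55% | 22 | 18 |
| 2% vs 10% | 24% | 41% | 17 | 12-14 |
| 2% vs 15% | 59-61% | 70-72% | 9-14 | 8-10 |
| 3% vs 15% | 52-53% | 60-64% | 8-11 | 6-8 |
| 5% vs 15% | 38-40% | 42-46% | 4-6 | 4-9 |
| 5% vs 20% | 64% | 66-68% | 3-4 | 4-6 |

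The size of the adjusted Firth test is 0.6-8.2% at common rates of 1-5%, so the gain does not come from exceeding 10%. Firth without the covariate gains 1-14 points by exact calculation; the covariate accounts for only part of the improvement.

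**The case against.** **The loss depends on rates the documents do not give.** A reader might infer a general loss of some 10-18 points, or that the test can hardly ever reject. The documents support neither. At 5% placebo the loss is 3-9 points, and planned power at n = 40 reaches 60% (2% vs 15%) and 65% (5% vs 20%). Empty cells are also less likely if short records count as seizure-free: mITT needs only one maintenance diary entry, and Table 11 sets no minimum diary coverage. This objection stands, and is why the loss is given as a range with its conditions.

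**Low size mostly reflects sparse counts.** Unadjusted Firth and Fisher mid-p also have sizes of only about 0-6% at rates of 1-5%. This stands: the fix removes only part of the undersizing.

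**The conflict with SAP 5.5 is not literal.** That rule concerns the baseline value of each efficacy variable. Given inclusion criterion 4, nobody is seizure-free at baseline, so that value is constant. The PGI-C row has no baseline term either. This stands in part: PGI-C has no pre-treatment score, whereas baseline seizure rate exists, and the responder model uses it for the same kind of outcome. Table 11 gives no reason for the difference.

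**Baseline rate as the main predictor is an assumption.** Neither document says so. Nor can Fisher be faulted for discarding a covariate, since the planned model has none.

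**The stakes are low.** This is one of seven other-secondary efficacy endpoints, in a trial that SAP 5.4 calls exploratory. That limits the importance of the point, but does not justify an estimate that may not exist.

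**Conclusion.** The point holds as a cheap improvement. Two parts need no assumed rates. The seizure-freedom row is out of line with the responder and seizure-rate models and with the general statement in 5.5. And when an arm has no seizure-free subject, the odds ratio and interval have no finite maximum-likelihood value, while the only remedy depends on a software convergence flag.

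The numerical size does rest on assumed rates. At placebo rates of 1-5%, an empty placebo cell has probability 67% down to 13% with 40 per arm, and 61% down to 8% with 50. With Fisher granted for every zero cell, true size is about 0-3% at common rates of 1-5%. The power lost against adjusted Firth is about 3-22 points: 12-22 for placebo 1-2% versus active 10%, 6-14 for 2-3% versus 15%, and 3-9 for placebo 5%. These figures also assume the baseline distribution and slopes in the working. No primary or key secondary conclusion is affected.

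**What to change.** In the seizure-freedom row of SAP Table 11, replace the model and its convergence-based fallback with Firth penalised logistic regression (the FIRTH option of PROC LOGISTIC), with treatment and ln(baseline focal seizure rate per week). Report odds ratios for each dose against placebo with profile penalised-likelihood 90% confidence intervals and p-values. Keep pairwise Fisher exact tests as a sensitivity analysis, run whether or not any model converges.

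The cost is the wording of one table row and one procedure option; the data are already collected. The downside is that the odds ratio becomes a penalised estimate conditional on baseline rate, which the report should state alongside the raw counts per arm. The change should be made before unblinding.
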